8.10.2.2 Night Time Awakenings

8.10.2.2.1 Night Time Awakenings Secondary to Hot Flashes

Night time awakenings secondary to hot flashes for Day Y = the sum of the number of moderate and severe night time hot flashes recorded on the continuous diary (as these are defined as resulting in a night time awakening) .

Frequency by day

The NTA secondary to hot flashes will be summarized for each day and displayed graphically by day. The change from Day -1 will also be summarized.

Average daily frequency by week

The average daily NTA secondary to hot flashes for Week 1 will be equal to the average of the NTA from Day 1 to Day 7. The average daily NTA secondary to hot flashes for Week 1 will be summarized by treatment.

The same statistical analyses for the daily scores as described in section 8.10.2.1 will be done based on the change from Day -1 NTA.

8.10.2.2 Night Time Awakenings - Total

The total NTA for Day Y = number of awakenings recorded on the continuous diary that are recorded as an awakening that is not accompanied by a hot flash + the number of night time moderate and severe hot flashes recorded.

The total NTA will be summarized for each day and displayed graphically by day. The change from Day -1 will also be summarized.

8.10.3 Sternal Skin Conductance Monitors

Frequency by day

The Day -1 frequency of hot flashes will be the number of hot flashes detected by the device from 24 hours before dosing on Day 1 to the dosing on Day 1. If there is >24 hours of recorded data, then only the 24-hour prior to the time of dosing on Day 1 will be used. If there is <24 hours of data recorded, then all the recorded data will be used and the actual recording duration will be used to derive a 24 hour value.

Postbaseline values will be based on 24-hour periods from the dose time on Day 1. If the recording time on Day 7 (or an earlier day in the event of early withdrawal) is <24 hours, then all the recorded data will be used and the actual recording duration will be used to derive a 24-hour value.

The number of algorithm-detected hot flashes (Bahr et al *Physiol Meas.* 2014 February ; 35(2): 95–110. doi:10.1088/0967-3334/35/2/95; algorithm commercial property of SimplexScientific LLC) will be summarized and displayed graphically for each day by treatment. The change from Day -1 will also be summarized.

Average daily frequency by week

The average daily frequency of hot flashes detected by the device for Week 1 will be equal to the average of the daily frequency of hot flashes detected by the device from Day 1 to Day 7 inclusive.

The average daily frequency for Week 1 will be summarized by treatment.

Statistical analysis

The same statistical analyses as described in Section 8.10.2.1 will be done for the change from Day -1 in the frequency of hot flashes detected by the device.

8.10.4 Luteinizing Hormone

The observed values on Day -1, Day 1, and Day 7, and change from Day -1 (for Day 1 and Day 7) data for continuous LH AUC₀₋₈ values will be summarized by treatment at each visit. The AUC₀₋₈ will be derived using the trapezoidal method and based on the actual times.

An analysis will be based on a linear mixed-effects model with the change from Day -1 as a dependent variable, treatment, day and treatment-by-day interaction as fixed effects, subject as a random effect and the AUC₀₋₈ value at Day -1 and the interaction with day as covariates. Subjects dosed with placebo will be analyzed as a pooled group. An unstructured covariance matrix will be specified for the repeated measures at postdose timepoints for each subject. From this analysis, the LS mean and 2-sided 90 % CIs will be calculated for the contrast “NT-814 versus placebo” at each treatment and each postdose day, separately.

Following is the SAS code for reference:

```
proc mixed data=dataset ;  
class TRT <50 mg NT-814, 100 mg NT-814, 150 mg NT-814, XX mg NT-814(2 further ascending doses up to 400mg), placebo>  
DAY <1,7> USUBJID;  
model CHG = TRT DAY TRT*DAY BSL BSL*DAY / s ddfm=kr;  
random USUBJID;  
repeated DAY / type=un subject=USUBJID;  
lsmeans TRT*DAY / cl diff alpha=0.1;  
run;
```

8.10.5 Relationship Between PK Exposure and Responses

The relationship between PK exposure and efficacy and pharmacodynamic responses will be investigated depending on what is seen in the response data. These analyses will be described in a separate document.

8.11 Analysis of Safety Data

8.11.1 General

All analyses will be performed using the safety set.

8.11.2 Adverse Events

All AEs will be coded to system organ class (SOC) and preferred term (PT) using MedDRA, Version 19.0, and presented by subject in data listings.

A treatment-emergent adverse event (TEAE) is defined as an AE that was not present prior to treatment with investigational product, but appeared following treatment or was present at treatment initiation but worsened during treatment. An AE that was present at treatment initiation but resolved and then reappeared while the subject was on treatment is a TEAE (regardless of the intensity of the AE when the treatment was initiated). Programmatically, an AE will be classified as a TEAE if the start date and time occurs on or after the start date and time of first investigational product dosing. Any change in severity will be recorded as a new AE in the eCRF. An AE with an incomplete start or end date will be considered a TEAE unless it is clear from the incomplete start and end date that the AE started before start of dosing.

The overall incidence of TEAEs (number and percentage of subjects with one or more TEAEs) as well as the number of events will be summarized by treatment received. Separate summaries by treatment received will also be presented showing TEAE severity, causally related TEAE and SAEs, TEAEs leading to study or treatment discontinuation, all SAEs, life-threatening SAEs, SAEs resulting in death and TEAEs of dehydration (changes in serum urea and creatinine, urinary sediment and weight and vital signs that the PI classifies to be an AE).

The TEAEs will be summarized and tabulated at both the subject (number [%] of subjects) and event (number of events) level:

- By treatment, SOC, and PT
- By treatment, SOC, PT, and reported severity
- By treatment, SOC, PT, and relationship to study drug

For the incidence at the subject level by SOC and PT, if a subject experiences more than one event within the same SOC and PT, the patient will only be included once in the incidence.

For the incidence at the subject level by SOC, PT, and severity, if a subject experiences more than one event within the same SOC, PT, the patient will only be included once in the incidence and will be assigned the worst severity.

For the incidence at the subject level by SOC, PT, and relationship to study drug; if a subject experiences more than one event within the same SOC, PT, to study drug, the patient will only be included once in the incidence and will be assigned the most conservative relationship.

Any SAEs, SAEs with outcome of death, AEs resulting in discontinuation of study or treatment, and TEAEs of dehydration will also be listed separately.

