10.6 Adverse events

In order to avoid bias in eliciting AEs, subjects should be asked a non-leading question, such as “How are you feeling?” It is also important to question the subject in a non-leading way about changes in their health or concomitant medication usage since their last visit. All AEs will be recorded from the time the informed consent is signed until study exit, and are recorded on the appropriate pages in the eCRF and in source documents. Appropriate follow-up will be required for any adverse events ongoing at study exit.

Serious Adverse Events (SAEs) occurring up to 30 days after the last dose of study medication should be reported.

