4.10.1.2 Severity and Relatedness Assessment

Severity will be classified as follows:

- Mild: Awareness of sign or symptom, but easily tolerated
- Moderate: Sign or symptom causes discomfort, but does not interfere with normal activities
- Severe: Sign or symptom of sufficient intensity to interfere with normal activities

The likely relationship of each AE to the medicinal product will be assessed according to the definitions below:

- Unrelated
- Possibly
- Probably
- Definitely

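### SAP 8.11.2: the programmed TEAE rule also flags pre-dose AEs that ease to a lower grade without resolving, which the SAP's own definition excludes

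*SAP*

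**What the plan says.** Three statements in one paragraph of SAP 8.11.2 matter here.

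- **Definition.** An AE is treatment-emergent if it "appeared following treatment or was present at treatment initiation but worsened during treatment". One extension follows: "An AE that was present at treatment initiation but resolved and then reappeared while the subject was on treatment is a TEAE". Easing of an AE that is still present is in neither.
- **Programmed rule.** In the data, "an AE will be classified as a TEAE if the start date and time occurs on or after the start date and time" of first dosing. There is no condition on severity and no link to an earlier record.
- **Recording rule.** "Any change in severity will be recorded as a new AE in the eCRF". This covers changes in either direction.

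TEAEs are then tabulated both by subject and by number of events. At subject level, each woman counts once per system organ class and preferred term.

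The setting allows the case to arise. Protocol 10.6 states: "All AEs will be recorded from the time the informed consent is signed until study exit". AEs that begin during the 4-week screening period or on Day -1 are therefore on file and may be ongoing at first dose. The severity scale in SAP 4.10.1.2 has three grades (mild, moderate, severe), so an AE can improve and still be recorded as present.

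**The concern.** The recording rule is what lets a simple date test work. If a mild pre-dose AE becomes moderate, a new record opens after dosing and the date test catches it, as the definition intends. But an improvement opens a new record in the same way, and the date test cannot tell the two apart. A moderate headache that began in screening and eased to mild on Day 2 would get a record starting on Day 2 and be programmed as a TEAE, although the subject's condition improved.

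Safety is part of the primary objective, and the TEAE tables are a main summary of it. The active groups have only 15 women each, so a single misclassified subject visibly moves a percentage. A programmer following the text literally would produce tables that disagree with the definition printed beside them.

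**Working it through.** The plan states no figure on this point, so there is nothing to reproduce. The check compares the definition with the programmed rule over every change in grade.

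**Inputs.** Grades none = 0, mild = 1, moderate = 2, severe = 3 (SAP 4.10.1.2). The definition, programmed rule and recording rule are from SAP 8.11.2. Group sizes are 15 active and 5 placebo per cohort, with placebo pooled across cohorts (SAP 8.12 and 8.1).

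**Rules as formulas**, for one change from the grade at first dose (pre) to an on-treatment grade (post):

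- Definition: TEAE if post > pre.
- Programmed rule: TEAE if post ≠ pre and post > 0. A change to a non-zero grade opens a record, and that record starts after first dose.

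There are 4 × 4 = 16 pairs. Dropping none-to-none leaves 15.

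| Change | Number of pairs | Definition | Programmed rule |
|---|---|---|---|
| New onset (none to any grade) | 3 | TEAE | TEAE |
| Worsening (mild to moderate, mild to severe, moderate to severe) | 3 | TEAE | TEAE |
| Unchanged grade | 3 | Not a TEAE | Not a TEAE |
| Complete resolution | 3 | Not a TEAE | Not a TEAE |
| Partial improvement (moderate to mild, severe to mild, severe to moderate) | 3 | Not a TEAE | **TEAE** |

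The two rules agree on 12 pairs and disagree on 3, all of them partial improvements. The extension for AEs that resolve and reappear does not cover these 3, because the AE never resolved. If a continuing record must also satisfy post > pre, the disagreements fall from 3 to 0.

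**Does another section repair it?**

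- Protocol 11.3.2 announces a treatment-emergent analysis but gives no definition or programming rule.
- Protocol 10.4.2 and SAP 4.10.6 send improvement of a medical-history finding to source documents, and give a stop date to a finding noted as an AE once it resolves. They do not address partial improvement of an AE.
- The once-per-subject rule in SAP 8.11.2 removes duplicates. It does not remove a woman whose only post-dose record under a term is the eased one.

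**Size per affected woman**, if she has no other TEAE:

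- Dose group: 1/15 = 6.7 percentage points.
- Pooled placebo, 4 cohorts: 4 × 5 = 20, and 1/20 = 5.0 points.
- Pooled placebo, 5 cohorts: 5 × 5 = 25, and 1/25 = 4.0 points.

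**The case against.** Much can fairly be said for leaving the text alone.

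**The route is narrow.** Complete resolution closes the existing record and creates no TEAE, and a mild AE can improve only by resolving. A reader might infer that every pre-dose AE that improves becomes a TEAE; the table shows otherwise. The false record is always mild or moderate, so counts of severe TEAEs are not raised by it. This stands and sets the scope of the point.

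**The frequency is unknown and may be low.** Findings identified at screening go to medical history, and Protocol 7.3 excludes several kinds of active or unstable disease and clinically significant laboratory abnormalities up to Day -1. A reader might apply an assumed rate: if 5%, 10% or 20% of women had such an AE, 15 × rate gives 0.75, 1.5 or 3 women per dose group. Neither document supports any of these rates. For overall incidence the products are also upper bounds, since a woman with another TEAE is counted anyway. This stands too.

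**The rule is the same in all arms and decides nothing.** Treatment is blinded, no primary hypothesis test is specified (Protocol 11), and the stopping criteria in Protocol 9.9 do not use the TEAE flag. The listing of all AEs would still show the pre-dose record. A reader might infer a bias against NT-814, for instance if it eased pre-existing symptoms. That is possible, but the documents give no evidence of it.

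**Event counts.** A reader might also object that one on-treatment AE changing grade is counted as several events: mild-moderate-mild gives three records, and mild-moderate-severe-moderate-mild gives five. The SAP discloses this convention and it does not conflict with the definition, so it is not an error.

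None of this removes the conflict between the definition and the programmed rule.

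**Conclusion.** The concern holds for partial improvement only. As written, SAP 8.11.2 would program three kinds of change as treatment-emergent that its own definition excludes. That conclusion follows from the text and depends on no assumed rate.

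The size can be stated only per case: 6.7 points in a 15-woman dose group and 5.0 or 4.0 points in pooled placebo. These figures assume that the planned numbers are dosed and that the woman has no other TEAE. For a single preferred term, the corresponding condition is that she has no other TEAE under that term. The documents do not support an estimate of the total inflation, or a claim that the dose comparison is biased in a particular direction.

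This is a real but contained error in a safety rule, and cheap to correct.

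**What to change.** Add to SAP 8.11.2 that a post-dose record continuing an AE ongoing at first dose is a TEAE only if:

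- its severity exceeds the severity at first dose, or
- the AE had resolved and then recurred.

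Identify a continuing record by same subject, same term and contiguous dates, or by an eCRF link field if one exists. The Data Management Plan is not among the documents, so whether such a field exists is unknown. Dates and terms alone may not separate a severity change from resolution and recurrence on the same day. Those cases should be reviewed blinded and settled before unblinding.

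The cost is a short change to the SAP, some programming and blinded review of a few records. If dates and terms are used, no new data item is needed. A table footnote saying that each severity change counts as a separate event would help readers, but is optional.

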8.11.3 Clinical Laboratory Assessments

Observed and change from baseline of continuous clinical laboratory values (chemistry, hematology, lipids, coagulation, and hormones including estradiol, testosterone, FSH, ACTH, cortisol, TSH, T3 and T4) for each parameter will be summarized by treatment at each time point. The number and percentage of subjects with shift changes from baseline based on the laboratory normal ranges will be tabulated.

Laboratory data will be listed by subject at each time point. Clinical laboratory values that are out of normal ranges will be presented in a separate listing.

Urinalysis laboratory tests will be presented in data listings only.

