7.3 Exclusion criteria

The following exclusion criteria will apply to all subjects:

1. Any active comorbid disease deemed by the investigator to be clinically significant which could impact safety during study conduct including renal or hepatic impairment:
 - a) Serum creatinine laboratory value greater than 1.2 times upper limit of normal (ULN) reference range (after adjustment for age) at Screening or Day -1 or subjects with renal function glomerular filtration rate (GFR) $<60\text{mL}/\text{min}/1.73\text{m}^2$ based on the MDRD equation.
 - b) Total bilirubin greater than upper limit of normal reference range (with the exception of Gilbert's Syndrome) and/ or alanine transaminase (ALT) >2 times ULN reference ranges and/ or aspartate amino transferase (AST) >2 times ULN reference ranges, at Screening or Day -1.
2. Subjects with a prior medical history of or an increased risk of seizures, or who have a history of recent (within 6 months of Screening) head trauma that resulted in a loss of consciousness or concussion
3. Any prior or ongoing history of arrhythmias
4. Any ongoing cardiovascular disease including heart failure, coronary artery disease or uncontrolled hypertension or uncontrolled diabetes
5. Any clinically relevant ECG abnormalities at Screening
6. Unwillingness to refrain from eating grapefruit, grapefruit juice, Seville oranges, and pomelos from 7 days prior to admission on Day -1 until after their final follow-up visit
7. Use of any prohibited medications (see Section 9.13.2)
8. Any history of invasive malignancy in the past 2 years
9. Any active ongoing condition that could cause difficulty in interpreting vasomotor symptoms such as: infection that could cause pyrexia, pheochromocytoma, hyperthyroidism, carcinoid syndrome, alcohol abuse
10. Body mass index (BMI) $> 35\text{kg}/\text{m}^2$
11. Inability to complete questionnaires for any reason including psychiatric disorders and inability or unwillingness to use electronic devices
12. History of hypothalamic dysfunction.
13. Any clinically significant or unstable medical or psychiatric condition that would interfere with the subject's ability to participate in the study including anxiety syndromes
14. Any clinically significant abnormal laboratory test result(s) at Screening or on Day -1.

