15. Participation in any clinical research study evaluating another investigational drug or therapy within 30 days or within 5 half-lives (whichever is longer), of the investigational drug prior to consenting to study entry. If the subject is in an observational clinical study no washout is required.
16. Subjects who, in the opinion of the Investigator, should not participate in the study for any other reason.
17. Any known allergy or hypersensitivity to any of the ingredients in the study medication or to skin adhesives.

Any clinical or laboratory readings that narrowly miss the exclusion criteria such as BMI, serum creatinine and liver function tests can be considered on a case by case basis for inclusion after discussion with the medical monitor.

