5. Two or more subjects, who have received NT-814, develop hypotension, defined as an asymptomatic fall in Systolic blood pressure (SBP) > 20 mmHg to below 70 mmHg persisting for at least 10 minutes, or a symptomatic fall in resting supine SBP > 20 mmHg (excluding vasovagal reaction or associated with hot flashes) deemed to be at least possibly related to study drug
6. One or more subjects, who have received NT-814, fulfill Hy's law, defined as "an increase in AST or ALT ≥ 3 x upper limit of normal (ULN) and total bilirubin (TBL) ≥ 2 x ULN, where no other reason can be found to explain the combination of increases, e.g., elevated serum alkaline phosphatase (ALP) indicating cholestasis, viral hepatitis, another drug. The elevations do not have to be at the same time or within a specified time frame"
7. Two or more subjects, who have received NT-814, have > 3 x ULN of either ALT or AST, or > 2 x ULN for bilirubin or ALP deemed to be at least possibly related to study drug
8. Two or more subjects, who have received NT-814, have clinical and biochemical signs suggesting dehydration as assessed by the Investigator and Sponsor (weight loss $> 10\%$ from baseline, loss of skin turgor and biochemical signs such as increased serum urea and creatinine, high urinary osmolality and sediment) deemed to be at least possibly related to study drug
9. Two or more subjects, who have received NT-814, have sustained oxygen saturations below 90% that does not increase after administration of supplemental oxygen, deemed to be at least possibly related to study drug.
10. Two or more subjects, who have received NT-814, with clinically relevant cardiovascular AEs such as ventricular tachycardia or atrial fibrillation deemed to be at least possibly related to study drug
11. Dose escalation will not occur if the exposure of NT-814 is predicted to exceed a geometric mean AUC of 20950 ng.h/mL

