14.5 Confidentiality

Study data will be handled with utmost discretion within the context of physician's confidentiality. On the eCRFs and other study specific documents, subjects are not identified by their names, but by a unique subject number. Names of participating subjects and data generated as a result of this study will not be passed on to unauthorized persons.

The Investigator must assure that the subjects are properly anonymized throughout the study. On all study documentation which is supposed to leave the site (i.e., to be transmitted to NeRRe, CRO or third parties), subjects will only be identified by their unique identification code and will not be referred to by name.

NeRRe may transfer some data collected during the study to a different company or regulatory authority outside of the US for the purpose of processing, review, analysis or storage. Whenever the subject's personal data is transferred, it will be kept confidential and secure, and will used only for the purpose for which it was collected.

Safety analysis samples collected during the study will be analyzed at the local hospital facility per local procedures. As such samples will not be leaving the local hospital laboratory facility; there will be no specific study requirements to make the samples anonymous. All safety samples will be destroyed after the assays have been completed.

NT-814 PK samples will be shipped to Aptuit Srl, Italy for analysis. Analysis will be conducted after each cohort with the results included in the final study report. Following completion of the analysis, all samples will be destroyed.

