Figure 14.2.1.5.1	Mean (+/- SE) Night Time Awakenings (Total) - Twice Daily Diary (Full Analysis Set)
Figure 14.2.2.1.1	Mean (+/- SE) Daily Frequency of Hot Flashes - Continuous Hot Flash Diary (Full Analysis Set)
Figure 14.2.2.2.1	Mean (+/- SE) Night Time Awakenings Secondary to Hot Flashes

	- Continuous Hot Flash Diary (Full Analysis Set)
Figure 14.2.2.3.1	Mean (+/- SE) Night Time Awakenings (Total) - Continuous Hot Flash Diary (Full Analysis Set)
Figure 14.2.3.1	Mean (+/- SE) Daily Frequency of Hot Flashes Detected by the Device - Sternal Skin Conductance (Full Analysis Set)
Section 14.3	Safety Data Summaries
Section 14.3.1	Displays of Adverse Events
Table 14.3.1.1	Overall Summary of Treatment-Emergent Adverse Events (Safety Set)
Table 14.3.1.2	Summary of Treatment-Emergent Adverse Events by System Organ Class and Preferred Term (Safety Set)
Table 14.3.1.3	Summary of Treatment-Emergent Adverse Events by Reported Severity (Safety Set)
Table 14.3.1.4	Summary of Treatment-Emergent Adverse Events by Relationship to Study Drug (Safety Set)
Section 14.3.2	Listings of Deaths, Other Serious and Certain Significant Adverse Events
Table 14.3.2.1	Listing of Adverse Events Leading to Death (Safety Set)
Table 14.3.2.2	Listing of Serious Adverse Events (Safety Set)
Table 14.3.2.3	Listing of Adverse Events Resulting in Discontinuation of Study or Treatment (Safety Set)
Table 14.3.2.4	Listing of Treatment-Emergent Adverse Events of Dehydration (Safety Set)
Section 14.3.4	Abnormal Laboratory Value Listing
Table 14.3.4.1	Listing of Abnormal Laboratory Results (Safety Set)
Section 14.3.5	Additional Safety Data Summaries
Table 14.3.5.1	Absolute and Change from Baseline for Clinical Laboratory Parameters (Chemistry, Hematology, Lipids and Coagulation)

	(Safety Set)
Table 14.3.5.2	Absolute and Change from Baseline for Laboratory Hormones Results (Safety Set)
Table 14.3.5.3	Laboratory Shift in Normal Range Indicator by Category (Chemistry, Hematology, Lipids and Coagulation) (Safety Set)
Table 14.3.5.4	Laboratory Shift in Normal Range Indicator of Hormones Results (Safety Set)
Table 14.3.5.5	Absolute and Change from Baseline Vital Signs (Safety Set)
Table 14.3.5.6	Summary Statistics of 12-Lead ECG Values and Change from Baseline (Safety Set)
Table 14.3.5.7.1.1	Summary of Daily Maximum QTcB and QTcF Interval Results (Safety Set)
Table 14.3.5.7.1.2	Summary of Overall Maximum Post-Baseline QTcB and QTcF Interval Results (Safety Set)

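### Laboratory shift tables use only normal-range categories, so no planned table counts, by dose and placebo, the women who reach the protocol's own liver limits

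*SAP*

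**What the plan says.** **Planned displays.** SAP 8.11.3 gives observed values and change from baseline by treatment and time point, a shift table, a full listing and a listing of out-of-range values. On shifts it says: "The number and percentage of subjects with shift changes from baseline based on the laboratory normal ranges will be tabulated". The table list in SAP section 9 matches this. Table 14.3.5.3 is titled "Laboratory Shift in Normal Range Indicator by Category (Chemistry, Hematology, Lipids and Coagulation", and no other table there uses multiples of ULN. Under SAP 8.1, baseline is the last value before the first dose, and unscheduled and repeat results are listed but left out of safety summaries.

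**Entry limits (protocol 7.3).** Exclusion 1b removes women with "alanine transaminase (ALT) >2 times ULN reference ranges" or "aspartate amino transferase (AST) >2 times ULN reference ranges, at Screening or Day -1". Raised bilirubin is also excluded, except in Gilbert's syndrome. Exclusion 14 removes women with "Any clinically significant abnormal laboratory test result(s) at Screening or on Day -1". The section then adds a waiver: "Any clinical or laboratory readings that narrowly miss the exclusion criteria such as BMI, serum creatinine and liver function tests can be considered" individually with the medical monitor.

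**Action limits.** Protocol 9.8 sets individual discontinuation at 3 x ULN or more for AST and ALT. Protocol 9.9 criterion 7 applies when two or more NT-814 subjects "have > 3 x ULN of either ALT or AST, or > 2 x ULN for bilirubin or ALP" and the change is at least possibly drug-related. Criterion 6 is Hy's law: AST or ALT at 3 x ULN or more with total bilirubin at 2 x ULN or more, not necessarily at the same time, and with no other explanation.

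**Laboratories.** Protocol 14.5 says that safety samples "will be analyzed at the local hospital facility per local procedures". The synopsis gives four centres.

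**The concern.** The protocol states its liver limits as multiples of ULN. The SAP classifies liver results only as inside or outside the normal range. The two scales meet at 1 x ULN and nowhere else, so the categorical table cannot show whether a woman came near 3 x ULN.

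Safety is half of the primary objective, and protocol 11.1 says the placebo women are there mainly as a safety reference. A reader of the study report will want to know how many women at each dose, and on pooled placebo, reached the limits the protocol treated as important. The planned tables do not answer that. They can give a small rise and a large one the same weight, and a dose-related pattern in large rises could be diluted.

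The SAP treats QTc differently. Section 8.11.5 tabulates maximum QTc and maximum change in bands that include the 500 msec and 60 msec values of stopping criterion 2. The liver criteria have no counterpart.

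**Working it through.** The plan states no figure on this point, so there is nothing to reproduce. The check classifies hypothetical ALT or AST pairs, in multiples of ULN, in two ways: by the SAP rule (high if above 1 x ULN) and by bands cut at the documents' own values of 1, 2 and 3 x ULN. No pair ends exactly at 3, so the choice between 'above' and 'at or above' does not affect the result.

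| Baseline | Post-dose | Ratio | SAP rule | Banded |
|---|---|---|---|---|
| 0.6 | 1.2 | 2.0 | normal to high | ≤1 to >1–2 |
| 0.6 | 3.5 | 5.8 | normal to high | ≤1 to past 3 |
| 1.2 | 1.3 | 1.1 | high to high | >1–2, unchanged |
| 1.2 | 3.5 | 2.9 | high to high | >1–2 to past 3 |
| 1.5 | 3.1 | 2.1 | high to high | >1–2 to past 3 |
| 2.0 | 3.01 | 1.5 | high to high | >1–2 to past 3 |
| 2.0 | 5.0 | 2.5 | high to high | >1–2 to past 3 |

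**Raised baseline.** For any baseline above 1 and up to 2 x ULN, every later value past 3 x ULN lands in the same cell as the 1.2 to 1.3 case. From the entry ceiling, a ratio of 3/2 = 1.5 is enough to reach 3 x ULN.

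**Normal baseline.** The first two rows share one cell although one ends at 1.2 and the other at 3.5 x ULN. This half of the problem does not depend on how many women enter with raised values.

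**Illustration in one arm of 15.** Suppose one woman goes from 1.5 to 6 x ULN and the rest do not change:
- effect on the mean change: (6 − 1.5)/15 = 4.5/15 = 0.30 x ULN
- change in the shift count: 0 of 15
- threshold count: 1/15 = 6.7%

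**How often a raised baseline might occur.** The documents do not give the share p of women above ULN at baseline. The chance of at least one among 15 active women is 1 − (1 − p)^15:

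| Assumed p | Chance of at least one |
|---|---|
| 2% | 26% |
| 5% | 54% |
| 10% | 79% |
| 20% | 96% |

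This is the chance of a raised baseline, not of a later rise past 3 x ULN.

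**Two further gaps.** Hy's law joins two analytes in the same woman, possibly at different times, so one-parameter tables by time point cannot show it. Scheduled post-dose chemistry is limited to Day 8, Day 14 and early termination (SAP 4.10.2), so a peak seen only on a repeat or unscheduled sample enters no laboratory summary.

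**The case against.** The strongest reply is that the information is available elsewhere and that nothing done during the trial depends on these tables. Much of this stands.

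- **Other displays.** A reader might infer that a woman past 3 x ULN can be found only in the abnormal-value listing. That is not so. SAP 8.1 includes the maximum in continuous summaries, so a scheduled peak can show in Table 14.3.5.1; in the illustration above, the value of 6 and the rise of 4.5 would probably be the arm's maxima. An abnormal laboratory result reported as an AE enters the TEAE tables. Protocol 7.4 lets laboratory results be a reason for discontinuation, and those cases enter the disposition and discontinuation displays.
- **Stopping rules.** A reader might infer that a stopping limit could be missed during the trial. The documents do not support this. Under protocol 9.9, events go to unblinded safety reviewers as they occur, and the Safety Review Committee reviews each cohort.
- **Eligibility.** Exclusion 14, and the reference to hepatic impairment in exclusion 1, narrow the raised-baseline group. They do not close it, because a value of 1 to 2 x ULN that is not judged clinically significant is still allowed.
- **Local ranges.** A reader might infer that pooled raw values are on different scales. The documents say only that analysis is local. They give no site ranges, units or methods, so differing limits are a possibility, not a fact.
- **Descriptive phase 1b study.** Protocol 11 specifies no primary hypothesis test and 11.3.2 asks for descriptive statistics. That is true, but a count by dose is descriptive.

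What the reply does not supply is the count itself. A maximum does not say how many women passed a limit, and it is not planned in multiples of ULN. AE tables depend on the investigator reporting the result as an event. Discontinuation tables depend on 9.8, which read literally requires both AST and ALT, whereas 9.9 criterion 7 requires either.

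**Conclusion.** The concern holds as a gap in end-of-study reporting. The planned shift tables cannot separate a rise past 3 x ULN from a trivial one, whether the woman starts above ULN or within range. No planned table gives, by dose and pooled placebo, the number of women reaching the liver limits of protocol 9.8 and 9.9 or the Hy's law combination.

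The size is modest. A single case in an active arm is 6.7% of 15 women and may leave the shift count unchanged. How often this would happen cannot be derived, because neither the share with raised baselines nor the rate of large rises is given. The conclusion assumes the usual low, normal and high reading of the normal-range indicator.

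It would go too far to say that liver signals are hidden, that the values are lost or that subject protection during the trial is weakened. The change is worth making because it is cheap, serves half of the primary objective, and follows what the SAP already does for QTc.

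**What to change.** In SAP 8.11.3 and section 9, add one table by treatment (each dose and pooled placebo):

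- Maximum post-baseline ALT, AST, ALP and total bilirubin, each divided by the reporting laboratory's ULN, with the number and percentage of women in each band.
- Cross-tabulation by baseline at or below ULN versus above ULN.
- A count of women meeting the Hy's law combination at any time, as defined in protocol 9.9 criterion 6. The clause on other explanations needs medical judgement, so the table should say whether it counts laboratory-defined or adjudicated cases.
- A statement that unscheduled and repeat values are included, as an exception to SAP 8.1.

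Take the cut-offs from the protocol, but only after the sponsor has reconciled its passages. Protocol 9.8 joins AST and ALT at 3 x ULN or more. Criterion 7 of 9.9 uses either one above 3 x ULN, and bilirubin or ALP above 2 x ULN. One is an individual rule and the other a cohort rule, but the conjunction and the inequality differ and would be programmed differently. This review does not say which is right.

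The cost is a short SAP edit, one extra table and a little programming. No new data are needed: the normal ranges and results are already planned for Listings 16.2.8.1 and 16.2.8.2.
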